11.2 Sample Size Considerations

The primary outcome measure for this trial is treatment completion rate. A treatment completion rate of 70% or above would be sufficient to consider this regimen for further study. To test the null hypothesis that the treatment completion rate is 0.50 against the alternative that it is 0.70 at the one-sided 0.0510 level with 0.90 power will require 38 evaluable patients. To allow for potential 15% dropout, 45 patients will be enrolled in the study.

We will recruit 45 participants from the AMC core sites in Africa over an estimated 2 year period of time and have a minimum of 1 year of follow-up. We anticipate that at least 50% of recruited participants will be Stage 3 and 4. This will be helpful in stratified analyses by stage and node positivity.

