11.0 STATISTICAL CONSIDERATIONS

11.1 Statistical Analysis Plan

Treatment completion rate will be estimated as proportion of all women who complete cisplatin of those who initiate cisplatin treatment. The binomial proportion and its 95% confidence interval will be used to estimate the treatment completion rate.

The screening ratio will be estimated as the number of patients screened divided by the number of patients enrolled on the study. The Poisson rate and its 95% confidence interval will be used to estimate the screening ratio.

The Kaplan-Meier method will be used to describe the progression-free survival (PFS) and overall survival (OS). We will generate KM curves for Stage I/II participants as well as Stage III/IV participants. The stratified log-rank test will be used to evaluate the association of HAART use, node positivity including enlarged pelvic nodes, stratified for stage. Those factors that are significantly associated with PFS and OS will be incorporated into a proportional hazards model. The one-year PFS and OS will be estimated using the cumulative proportion progression free (for PFS) or surviving (for OS) and its 95% confidence interval.

Frequency tables will be used to summarize the occurrences of adverse events by severity grade. Frequencies of specific adverse events will be tabulated.

Toxicity assessment: All toxicities will be reported on standard case report forms at visits and graded by NCI CTC v4.0. There will be standard dose reduction schedules. All dose delays, dose reductions, and missing doses will be tracked via CRFs during therapy. These will be tabulated and reported as rates.

Adherence assessments are planned weekly during cisplatin therapy and at the end of protocol therapy. Participants will be considered inadherent to ARV if they report missing doses on more than one adherence assessment. The proportion of participants who were inadherent to ARV during protocol therapy will be estimated using the binomial proportion and its exact 95% confidence interval.

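### Section 11.2 sets a 70% completion statement beside a test of 0.50 against 0.70 without a critical count; the two readings need 27 and 25 completers of 38, and neither has the stated 0.90 power

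*Combined protocol and SAP*

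**What the plan says.** Section 11.2 names treatment completion as the primary outcome measure and makes two statements about it in succession.

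- A statement about further study: "A treatment completion rate of 70% or above would be sufficient to consider this regimen for further study".
- A hypothesis test: "To test the null hypothesis that the treatment completion rate is 0.50 against the alternative that it is 0.70". The level is given as 0.0510, one-sided, and a power of 0.90 is said to need 38 evaluable women. Enrolment is then inflated: "To allow for potential 15% dropout, 45 patients will be enrolled in the study".

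The analysis text in section 11.1 has no test of completion. It says: "The binomial proportion and its 95% confidence interval will be used to estimate the treatment completion rate". It does not name the interval method, although the same section calls for an exact interval for ART adherence.

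No section gives a critical number of completers, says that rejecting 0.50 is the condition for going on, or says how the 70% statement relates to the test.

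**The concern.** The 70% figure is also the design alternative. If the observed rate must reach the alternative, a regimen whose true rate equals the alternative passes only about half the time, at any sample size. The printed 0.90 power belongs to a different rule, rejection of 0.50, whose cut-off lies below 70%.

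Section 11.1 plans no test, so the person holding the final estimate has two figures to set it against, 0.50 and 70%, and no instruction on which one decides. Section 1.0 says that the completion estimate will inform planning of a phase II trial. A result between the two cut-offs could be reported as supporting further study or as falling short, and the choice could be made after the data are seen.

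**Working it through.** **Inputs (section 11.2):** null rate 0.50, alternative 0.70, one-sided alpha 0.0510, power 0.90, 38 evaluable, 15% dropout, 45 enrolled. The 70% statement comes from the same section and the 95% interval from section 11.1.

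**1. The plan's own figure.** Normal approximation: n = [(z_alpha × √(p0·q0) + z_beta × √(p1·q1)) / (p1 − p0)]².

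- Alpha 0.0510: [(1.635 × 0.5 + 1.282 × 0.458) / 0.20]² = 49.3, so 50. This does not give 38.
- Alpha 0.10: [(1.282 × 0.5 + 1.282 × 0.458) / 0.20]² = 37.7, so 38, with approximate power 0.902.
- At n = 38 and alpha 0.0510, approximate power is 0.82.
- Exact binomial with alpha at most 0.0510 first reaches 0.90 power at n = 53 (at least 33 completers: alpha 0.049, power 0.914).
- Dropout: 38 / 0.85 = 44.7, so 45, which agrees with the plan.

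The printed 0.90 therefore does not go with 0.0510 and 38. That 0.10 was the intended level is an inference from n = 38; the documents do not say so.

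**2. Exact rules at n = 38.** False-go is P(X ≥ r) at 0.50; power is P(X ≥ r) at 0.70.

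| Minimum completers r | Observed rate | False-go at 0.50 | Power at 0.70 |
|---|---|---|---|
| 23 | 60.5% | 0.128 | 0.924 |
| 24 | 63.2% | 0.072 | 0.863 |
| 25 | 65.8% | 0.036 | 0.774 |
| 26 | 68.4% | 0.017 | 0.659 |
| 27 | 71.1% | 0.007 | 0.524 |

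- 70% as an observed threshold: 0.70 × 38 = 26.6, so r = 27 and power is 0.524.
- Test at one-sided 0.0510: the smallest r with false-go at most 0.0510 is 25, with power 0.774.
- Test at one-sided 0.10, if that was intended: r = 24, with power 0.863.

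**3. The zone of disagreement.** At a true rate of 0.70, P(25 or 26 completers) = 0.774 − 0.524 ≈ 0.25. These results reject 0.50 at 0.0510 and fall below 70%. If alpha is 0.10, the zone is 24 to 26 completers, with probability 0.863 − 0.524 ≈ 0.34.

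**4. Would a larger n remove it?** No. At n = 53 the test has power 0.914, but an observed rate of 70% needs 38 completers and has power 0.460. If all 45 enrolled women are evaluable, an observed 70% needs 32 (power 0.509), while the test at 0.0510 needs 29 (alpha 0.036, power 0.836).

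**5. The interval in section 11.1.** Whether a 95% interval excludes 0.50 depends on the method. The exact interval for 25/38 has lower limit 0.486 and for 26/38 has 0.513; a simple normal interval for 25/38 has 0.507. The planned interval does not settle which count is a go.

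**The case against.** A reader might infer that 70% is the trial's go criterion, so that the trial has 52% power instead of 90% and discards a regimen with a true 70% completion rate about half the time. The documents do not support that.

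- The wording makes 70% sufficient, not necessary. No section says that a lower observed rate is a no-go.
- The text does not say whether the rate is observed or true. The statement stands in the sample size section directly before 0.70 is used as the alternative, so it can well be read as the reason for choosing that alternative.
- It is not the only criterion. The test is also specified, and the 0.90 is attached to the test.
- The contrast of 0.524 with 0.90 mixes two problems. Of the 38 points, about 13 (0.90 − 0.774) come from the mismatch of alpha, power and n; the other 25 (0.774 − 0.524) come from the choice of rule, and only if 70% is an observed threshold.
- Feasibility is also judged on the screening ratio and the availability proportion, and safety is a further primary objective (section 2.2). No automatic decision on one count is described.

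All of this stands, and it limits the point to an ambiguity. It does not remove it. If 70% is the true rate of interest, no section says that rejecting 0.50 is the go rule or how many completers that takes. If 70% is sufficient but not necessary, the standing of 25 or 26 completers is undefined. On either reading, the printed 0.90 is not what 38 women deliver at 0.0510.

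**Conclusion.** The point holds as an unresolved decision rule for the primary outcome, together with a power figure that neither reading delivers. With 38 evaluable women, the observed-70% reading needs 27 completers (power 0.524, false-go 0.007) and the test as printed needs 25 (power 0.774, alpha 0.036). At a true rate of 0.70, about one trial in four would end with 25 or 26 completers, where the two readings part.

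These figures assume an exact binomial test, a denominator of exactly 38, and 0.0510 as the intended level. If 0.10 was intended, the test's count becomes 24, with alpha 0.072 and power 0.863, still short of 0.90. That an observed 70% was meant as the bar is not established, so 52% should not be quoted as the trial's power.

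**What to change.** 1. Reconcile the printed alpha first, because the critical count depends on it: 0.0510 gives at least 25 of 38 (power 0.774); 0.10 would give at least 24 of 38 (alpha 0.072, power 0.863).
2. In section 11.2, make rejection of the null rate of 0.50 at that level the stated go rule for completion, and print its minimum number of completers. Add a rule for other denominators: the smallest count whose exact tail probability at 0.50 does not exceed the chosen alpha.
3. Say that 70% is the true rate the trial is designed to detect, not the observed cut-off.
4. Print the chosen rule's exact power and false-go rate in place of 0.90.
5. In section 11.1, cite the same rule and match the interval to the test level, naming the method. A one-sided 0.0510 test corresponds to a two-sided exact interval of 1 − 2 × 0.0510 = 89.8%; a one-sided 0.10 test corresponds to 80%.
6. If an observed 70% really is the bar, say so and print its power of 0.52.

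The change should be made before completion results are known. It needs no new data or procedures. Apart from settling alpha, it costs wording in two sections, and the stated power becomes less favourable.

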11.3 Site(s) of Recurrence

The site(s) of first disease recurrence will be classified as: pelvic-only, extrapelvic-only or pelvic-and-extra-pelvic or no recurrence and tabulated by treatment group. The test of the hypotheses that first site of recurrence is independent of randomized treatment will be assessed with a logistic model adjusted for FIGO stage, tumor size, lymph node involvement and type of brachytherapy. In addition, empirical plots of cumulative incidence of recurrence will summarize incidence of recurrence by treatment arm.

11.4 Toxicity Analysis

The toxicity data will be tabulated by treatment. The scale will be the Common Toxicity Criteria grading system (i.e., 1-5), but combining Grades 1 and 2. Five toxicity categories (CTCAE v4.0) will be tested: gastrointestinal (nausea, vomiting diarrhea), genito-urinary (acute toxicity manifested by cystitis, and acute vaginitis), and dermatologic (inguinal area, vulva, perineum, acute rash/desquamation, generalized macular, vesicular eruptions, and ulcerative dermatitis), blood/bone marrow and neurologic toxicities. Fisher's exact test will be employed to assess observed frequency differences for (incidence of maximum grade) specific adverse events by treatment arm.

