7.3 Routine AE Reporting

All AEs reported through CTEP-AERS must also be reported in routine study data submissions using the Adverse Event electronic case report form (eCRF). All AEs, except for expected Grade 1 events listed below, should be reported. All deaths that occur on study should be reported in the Adverse Event form and the Death Form, regardless of attribution to the protocol agents.

The following grade 1 AEs will not require reporting in the Adverse Event eCRF.

Grade 1 Expected Adverse Events for Radiation Therapy (listed by CTCAE Category and term):

GASTROINTESTINAL DISORDERS: diarrhea, proctitis, rectal pain

INJURY, POISONING AND PROCEDURAL COMPLICATIONS: dermatitis radiation

RENAL AND URINARY DISORDERS: urinary tract pain, cystitis noninfectious

REPRODUCTIVE SYSTEM AND BREAST DISORDERS: dyspareunia, pelvic pain, vaginal pain

SKIN AND SUBCUTANEOUS TISSUE DISORDERS: skin hyperpigmentation, skin hypopigmentation, alopecia

Grade 1 Expected Adverse Events for Cisplatin:

BLOOD AND LYMPHATIC SYSTEM DISORDERS: anemia

EAR AND LABYRINTH DISORDERS: tinnitus

GASTROINTESTINAL DISORDERS: nausea, constipation, diarrhea, abdominal pain

GENERAL DISORDERS AND ADMINISTRATION SITE CONDITIONS: fatigue

INVESTIGATIONS: creatinine increased, weight loss

METABOLISM AND NUTRITION DISORDERS: anorexia

NERVOUS SYSTEM DISORDERS: dysgeusia, paresthesia

SKIN AND SUBCUTANEOUS TISSUE DISORDERS: alopecia

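### Section 11.4 pools Grades 1 and 2 although Section 7.3 makes entry of listed Grade 1 events optional, so the pooled row can undercount exempt terms and is not comparable across terms

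*Combined protocol and SAP*

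**What the plan says.** Section 11.4 (Toxicity Analysis) tabulates toxicity in five categories: gastrointestinal, genito-urinary, dermatologic, blood/bone marrow and neurologic. On the scale it says: "The scale will be the Common Toxicity Criteria grading system (i.e., 1-5), but combining Grades 1 and 2". For specific events it works with the incidence of the maximum grade.

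Section 7.3 (Routine AE Reporting) gives the collection rule: "All AEs, except for expected Grade 1 events listed below, should be reported". It introduces the list with "The following grade 1 AEs will not require reporting in the Adverse Event eCRF". The entries include, for radiation, "GASTROINTESTINAL DISORDERS: diarrhea, proctitis, rectal pain", "RENAL AND URINARY DISORDERS: urinary tract pain, cystitis noninfectious" and "INJURY, POISONING AND PROCEDURAL COMPLICATIONS: dermatitis radiation", and for cisplatin "GASTROINTESTINAL DISORDERS: nausea, constipation, diarrhea, abdominal pain". The cisplatin list also names anemia, paresthesia and dysgeusia. The same section requires every event that has an expedited report to be on the eCRF as well.

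Section 11.1 (Statistical Analysis Plan) says: "All toxicities will be reported on standard case report forms at visits and graded by NCI CTC v4.0". It also plans frequency tables of adverse events by severity grade, with no pooling.

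Neither 11.1 nor 11.4 mentions the exemption.

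**The concern.** A row labelled Grade 1-2 implies that both grades were collected. For the exempt terms only Grade 2 is sure to be there, and a woman whose worst diarrhea is Grade 1 can appear in the table as having had none. Because entry is optional, completeness may also differ between sites. Once the two grades are added together, a reader of the 11.4 table cannot separate the complete part from the incomplete part.

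Safety and tolerability are a primary objective (2.2.2), and hypothesis 2.1.2 sets toxicity against that reported in HIV-uninfected women. Anyone who places the pooled row beside a published Grade 1-2 rate would compare unlike quantities. For exempt terms the error runs in one direction, making low-grade toxicity look rarer than it was.

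**Working it through.** The plan states no figure to reproduce here. The check compares the sections and then bounds the shortfall.

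**Step 1: the exempt list against the 11.4 categories.**

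| 11.4 category | Grade 1 exempt under 7.3 | Not on the exempt list |
|---|---|---|
| Gastrointestinal | nausea, diarrhea | vomiting |
| Genito-urinary | noninfectious cystitis | vaginitis |
| Dermatologic | radiation dermatitis | generalized eruptions, ulcerative dermatitis |
| Blood/bone marrow | anemia | neutropenia, thrombocytopenia |
| Neurologic | paresthesia, dysgeusia | peripheral neuropathy |

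Every category holds at least one exempt term and at least one that is not. The gastrointestinal category shows the difficulty best. Section 11.4 names nausea, vomiting and diarrhea together, and the pooled row would have one meaning for vomiting and another for the other two.

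**Step 2: what the row contains.** Let N be the number of women, g1 and g2 the shares whose maximum grade for a term is 1 or 2, and c the fraction of exempt Grade 1 events that sites enter anyway.

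- True Grade 1-2 count: N × (g1 + g2)
- Count shown for an exempt term: N × (c × g1 + g2)
- Fraction of the pooled count missing: (1 − c) × g1 / (g1 + g2)
- Non-exempt term: c = 1, so nothing is missing

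As a share of all women, the shortfall is (1 − c) × g1. Its upper bound is g1, reached only if no exempt event is entered.

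**Step 3: illustration.** N = 45 is the planned enrolment (Section 11.2). The rates are assumptions, because the documents give none. Take g1 = 0.40 and g2 = 0.20.

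- True count: 45 × (0.40 + 0.20) = 27
- Exempt term, c = 0: 45 × 0.20 = 9 shown; 18/27 = 67% missing
- Exempt term, c = 0.5: 45 × (0.20 + 0.20) = 18 shown; 9/27 = 33% missing
- Non-exempt term with the same rates: 27 shown

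**Step 4: range.** Let g1 run from 0.20 to 0.50, g2 from 0.10 to 0.30 and c from 0 to 0.5.

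- Smallest loss (g1 = 0.20, g2 = 0.30, c = 0.5): 0.5 × 0.20 / 0.50 = 20%
- Largest loss (g1 = 0.50, g2 = 0.10, c = 0): 0.50 / 0.60 = 83%

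**Step 5: whether 11.1 closes the gap.** Its sentence on case report forms is general, whereas 7.3 is a specific, itemised instruction on what goes into the Adverse Event eCRF. The documents describe no separate toxicity form that would collect the exempt events. The sentence therefore conflicts with 7.3 and does not restore the data. The by-grade tables of 11.1 have the same gap in their Grade 1 row, but their Grade 2 row is complete.

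**The case against.** The strongest reply is that little is lost. Five parts of it deserve an answer.

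- **Clean counts exist elsewhere.** The unpooled tables in 11.1 give Grade 2 on its own, and Grade 2 or worse follows by addition. This stands. It limits the harm to the 11.4 table and to readers who rely on it.
- **The exemption permits entry.** Sites may still record exempt events, and must do so when an expedited report was filed. Under Section 7.2 that covers a serious Grade 1 event with hospitalization of at least 24 hours. This also stands. A reader might infer that every exempt Grade 1 event is missing; the documents support that only as an upper bound.
- **The reach is uneven.** In the blood category only anemia is exempt, and Grade 1 anemia could be derived from the weekly CBC (Section 5.2.1), although no derivation is planned. Nausea, diarrhea, cystitis, dermatitis and paresthesia have no comparable laboratory source. Vaginal pain is exempt, but 11.4 names vaginitis, so it should not be counted as a match.
- **The safety conclusions rest on other data.** Section 9.1.4 judges tolerability by delays, reductions, missed doses and compliance. The dose-limiting toxicities in 6.2.2 are Grade 3 or 4 or worse. No planned analysis sets a Grade 1-2 row against published rates. The comparison by arm in 11.4 has no second arm to use in a single-arm study, so the row is descriptive. A reader might infer that the primary safety assessment is biased; the documents do not support that.
- **A footnote would do.** It would prevent the misreading, but it would leave a row that still mixes a complete count with an incomplete one. Separating the grades costs hardly more.

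**Conclusion.** The inconsistency is real and the consequence modest. As written, 11.4 gives a low-grade row that is undercounted by an unknown amount for exempt terms and is complete for the rest, under one label. The shortfall is at most the share of women whose worst grade is an exempt Grade 1 event. The 20% to 83% range rests wholly on the assumed rates and entry fractions and does not predict this trial's results. That the row means different things for different terms follows from 7.3 and 11.4 alone and needs no assumed rate.

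The Grade 3, 4 and 5 rows, dose-limiting toxicities, the 9.1.4 measures and the treatment completion endpoint are untouched. The change is still worth making, because it corrects a misleading safety row with data already being collected.

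**What to change.** - **Section 11.4:** do not pool Grades 1 and 2. Tabulate Grades 2, 3, 4 and 5 separately, in line with the by-grade tables of 11.1, and add summaries of Grade 2 or worse and Grade 3 or worse. Show Grade 1 only for terms not exempt under 7.3, with a footnote citing that section.
- **Section 11.1:** reword the case report form sentence to state the 7.3 exemption, and put the same footnote on the Grade 1 row of its tables.

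The cost is revised table shells and a few lines of wording, with no new data and no change to what sites collect. Section 11 is protocol text, so the change needs a written amendment under Section 12.2. It can travel with another amendment and should be settled before the tables are produced.

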12.0 ETHICAL AND REGULATORY CONSIDERATIONS

12.1 IRB/IEC Review and Informed Consent

The principles of IRB/IEC review and informed consent described in the Department of Health and Human Services (DHHS) regulations for the Protection of Human Subjects (45 CFR part 46) must be followed. IRB/IEC approval of the protocol and the informed consent form must be given in writing before research may commence at the institution.

The sponsor must receive a copy of the letter of approval from the IRB/IEC, which specifically approves the protocol and informed consent, before subject enrollment. The IRB/IEC must also approve any significant changes to the protocol and documentation of this approval must be sent to the sponsor. The IRB must review the research project at least once every 365 days during the duration of the project. Continuing approval of the project must also be given in writing and provided to the sponsor.

Records of all study review and approval documents must be kept on file by the Investigator and are subject to inspection during or after completion of the study. AEs must be reported to the IRB/IEC. The IRB/IEC should receive notification of completion of the study and final report within 3 months of study completion and termination. The Investigator will maintain an accurate and complete record of all submissions made to the IRB/IEC, including a list of all reports and documents submitted.

Written informed consent will be obtained from the subject. The nature, significance and risks associated with the study must be explained to the subject. The informed consent will describe the purpose of the study, the procedures to be followed and the risks and benefits of participation. A copy of the consent form will be given to the subject to keep.

In addition, any institution(s) conducting research according to the guidelines of this protocol is required to adhere to local and national laws and regulations governing the confidentiality and disclosure of health information.

12.2 Changes to the Protocol and Informed Consent Form

Any change or addition to this protocol or the model informed consent requires a written protocol amendment that must be approved by CTEP and the Investigator before implementation. Amendments significantly affecting the safety of subjects, the scope of the investigation or the scientific quality of the study, require additional approval by the IRB/IEC and national regulatory body approval depending upon the local regulations. All versions of the local informed consent form and any other written patient materials must also be approved by the IRB/IEC before presenting any such documents to participants. A copy of the written approval of the IRB/IEC and the national regulatory body (if applicable) must be sent to the ODMC for every protocol amendment and consent modification.

